### **9.2.2.3. Thyroid Malignancies and C-Cell Hyperplasia**

Individuals with personal or family history of MTC and/or MEN 2 will be excluded from the study, as well as those with values  $\geq 20$  pg/mL at screening. The assessment of thyroid safety during the study will include reporting of any case of thyroid malignancy including MTC and papillary carcinoma and measurements of calcitonin. This data will be captured in the specific section of the eCRFs. The purpose of calcitonin measurements is to assess the potential of study treatments to affect thyroid C-cell function, which includes development of C-cell hyperplasia and neoplasms.

Subjects who develop calcitonin increases  $\geq 50\%$  of the mean of the screening value AND an absolute value  $\geq 20$  pg/mL and  $< 35$  pg/mL after randomization, will be asked to repeat the measurement within 1 month. If this repeat value is increasing ( $\geq 10\%$  increase), the subject will be encouraged to undergo additional endocrine assessment and longer term follow-up by an endocrinologist to exclude a serious adverse effect on the gland. Subjects who develop calcitonin increases  $\geq 50\%$  of the mean of the screening value AND an absolute value  $\geq 35$  pg/mL after randomization will immediately undergo additional endocrine assessment and longer term follow-up by an endocrinologist. Investigational product should be discontinued in situations when post randomization calcitonin value is  $\geq 35$  pg/mL. If the calcitonin value decrease below 35 pg/mL on repeat tests, IP should be restarted if, in the opinion of the investigator, it is safe to do so. If the increased calcitonin value is observed in a subject who has administered a medication that is known to increase serum calcitonin, this medication should be stopped and calcitonin levels should be measured after an appropriate washout period.

For subjects who require additional endocrine assessment because of increased calcitonin concentration per criteria provided in this section, data from the additional assessment will be collected in the specific section of the eCRF.

#### **9.2.2.4. Major Adverse Cardiovascular Events**

Deaths and nonfatal CV AEs will be adjudicated by a committee of physicians external to Lilly with cardiology expertise. The nonfatal CV AEs to be adjudicated include the following:

- myocardial infarction
- hospitalization for unstable angina
- hospitalization for heart failure
- coronary interventions (such as coronary artery bypass graft or percutaneous coronary intervention)
- cerebrovascular events, including cerebrovascular accident (stroke) and transient ischemic attack

#### **9.2.2.5. Supraventricular Arrhythmias and Cardiac Conduction Disorders**

Treatment-emergent cardiac conduction disorders should be further evaluated. Subjects who develop any event from this group of disorders should undergo an ECG. Additional diagnostic tests to determine exact diagnosis should be performed, as needed. The specific diagnosis will be recorded as an AE. Events that meet criteria for serious conditions as described in Section 9.2.1 (Serious Adverse Events) must be reported as SAEs.

#### **9.2.2.6. Hypersensitivity Events**

All allergic or hypersensitivity reactions will be reported by the investigator as either AEs or, if any serious criterion is met, as SAEs. Additional data, such as type of reaction and treatment received, will be collected for any AEs or SAEs that the investigator deems related to IP via a eCRF created for this purpose. Additional serum samples should also be collected as outlined in Section 9.6.1 (Immunogenicity Assessments). IP should be temporarily interrupted in any individual suspected of having a severe or serious allergic reaction to IP. IP may be restarted when/if it is safe to do so, in the opinion of the investigator. If IP is permanently discontinued, the subject will receive another glucose-lowering treatment, judged by the investigator to be appropriate based on the subject's clinical status, and will be discontinued from the study (Section 8.1.1 Permanent Discontinuation from Study Treatment).

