- [25] Have a Patient Health Questionnaire-9 (PHQ-9) score of 15 or more at screening;
- [26] On the Columbia-Suicide Severity Rating Scale (C-SSRS) at screening:
  - a “yes” answer to either Question 4 (Active Suicidal Ideation with Some Intent to Act, Without Specific Plan) or
  - a “yes” answer to Question 5 (Active Suicidal Ideation with Specific Plan and Intent) on the “Suicidal Ideation” portion of the C-SSRS, or
  - a “yes” answer to any of the suicide-related behaviors (Actual Attempt, Interrupted Attempt, Aborted Attempt, Preparatory Act or Behavior) on the “Suicidal Behavior” portion of the C-SSRS, and
  - the ideation or behavior occurred within the past month
- [27] Have a history of atopy or clinically significant multiple or severe drug allergies, or severe posttreatment hypersensitivity reactions (including, but not limited to, erythema multiforme major, linear immunoglobulin A dermatosis, toxic epidermal necrolysis, or exfoliative dermatitis).

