#### **Prior/Concurrent Clinical Trial Experience**

- [33] Are persons who have previously completed or withdrawn from this study;
- [34] Have previous exposure to tirzepatide or known allergies to tirzepatide or GLP-1 receptor agonists;
- [35] Are currently enrolled in a clinical study involving an IP or any other type of medical research judged not to be scientifically or medically compatible with this study.

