## 7.3. Blinding

This study is a sponsor (study team members directly involved in study management)-, investigator-, and subject-blind study. Blinding will be maintained throughout the conduct of the study as described in the separate Blinding and Unblinding Plan. To preserve the blinding of the study for treatment allocation, all study site personnel, except site staff who dispense and administer study medication, will be blinded to treatment allocation. Tirzepatide and placebo will be dispensed by the site pharmacy in accordance to the randomization table. The site staff will take the necessary steps to ensure that subjects will remain blinded to the treatment administration.

If a subject's study treatment assignment is unblinded, the subject must be discontinued from the study, unless the investigator obtains specific approval from a Lilly clinical pharmacologist (CP) or clinical research physician (CRP) for the subject to continue in the study. During the study, emergency unblinding should occur only by accessing the subject's emergency code.

In case of an emergency, the investigator has the sole responsibility for determining if unblinding of a subject's treatment assignment is warranted for medical management of the event. The subject's safety must always be the first consideration in making such a determination. If the investigator decides that unblinding is warranted, it is the responsibility of the investigator to promptly document the decision and rationale and notify Lilly as soon as possible.

Upon completion of the study, all codes must be returned to Lilly or its designee.

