## **7.7. Concomitant Therapy**

Section 6.2 (Exclusion Criteria) provides excluded medications in this study prior to randomization (glucose-lowering and weight-lowering agents, systemic glucocorticoids). These medications are also not allowed during the treatment period. Erroneous use of excluded medications for up to 14 days would not qualify for discontinuation. If used for  $>14$  days during the entire treatment period or for any duration during the final 4 weeks of the treatment period, these subjects will discontinue treatment immediately and will be discontinued from the study after performing the early termination (ET) and safety follow-up visits. Subjects who use any of the medications from these classes for  $<14$  days any time prior to the final 4 weeks of the

treatment period will be requested to stop these treatments and will be allowed to continue in the study.

Subjects on stable concomitant medication at the time of study entry, other than those that are prohibited, should continue their regular, unchanged dose throughout the study. These medications include hormone replacement therapy (stable for at least 3 months), blood pressure medication, and statins.

Additional drugs are to be avoided during the study unless required to treat an AE or for the treatment of an ongoing medical problem. Acetaminophen (1 g, maximum 3 g/24 hours) may be administered at the discretion of the investigator for treatment of headaches or other conditions associated with pain. If the need for concomitant medication, other than acetaminophen arises, inclusion or continuation of the subject may be at the discretion of the investigator after consultation with a Lilly CP or CRP. Any medication used during the course of the study must be documented in source documents and transcribed into the eCRF.

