### 8.1. Discontinuation from Study Treatment

#### 8.1.1. Permanent Discontinuation from Study Treatment

Possible reasons leading to permanent discontinuation of IP:

- The subject requests to discontinue IP
- If a subject is inadvertently enrolled and it is determined that continued treatment with IP would not be medically appropriate (Section 8.1.3 Discontinuation of Inadvertently Enrolled Subjects)
- If a subject is diagnosed with acute or chronic pancreatitis after randomization
- If a subject is diagnosed with MTC after randomization
- If a subject is diagnosed with an active or untreated malignancy (other than basal or squamous cell skin cancer, in situ carcinomas of the cervix, or in situ prostate cancer) after randomization
- If a subject is diagnosed with a significant IP-related hypersensitivity reaction
- If a subject is diagnosed with any other TEAE, SAE, or clinically significant laboratory value for which the investigator believes that permanent IP discontinuation is the appropriate measure to be taken
- If female subject becomes pregnant

Discontinuation of the IP for abnormal liver tests **should be considered** by the investigator when a subject meets 1 of the following conditions after consultation with the Lilly designated medical monitor:

- ALT or AST >8X ULN for healthy subjects
- ALT or AST >5X ULN for more than 2 weeks or
- ALT or AST >3X ULN and TBL >2X ULN or international normalized ratio >1.5 or
- ALT or AST >3X ULN the appearance of fatigue, nausea, vomiting, right upper quadrant pain or tenderness, fever, rash, and/or eosinophilia (>5%)
- Alkaline phosphatase (ALP) >3X ULN
- ALP >2.5X ULN and TBL >2X ULN
- ALP >2.5 ULN with the appearance of fatigue, nausea, vomiting, right quadrant pain or tenderness, fever, rash, and/or eosinophilia (>5%).

- Drug-related vomiting requiring intravenous (IV) hydration treatment or causing severe distress (prevents daily activities and results in no appetite, or requires an emergency department visit, or hospitalization), that cannot be resolved by temporary interruption of IP (Section 8.1.2 Temporary Interruption of IP).

Subjects who discontinue IP early will be also discontinued from the study after performing the ET visit and safety follow-up visit procedures, as specified in Section 2 (Schedule of Activities).

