**9.2.2.2. Pancreatitis**

Acute pancreatitis is defined as an AE of interest in all studies with tirzepatide including this study. Acute pancreatitis is an acute inflammatory process of the pancreas that may also involve peripancreatic tissues and/or remote organ systems (Banks and Freeman 2006). The diagnosis of acute pancreatitis requires 2 of the following 3 features:

- abdominal pain, characteristic of acute pancreatitis (generally located in the epigastrium and radiates to the back in approximately half the cases [Banks and Freeman 2006; Koizumi et al. 2006]; the pain is often associated with nausea and vomiting);
- serum amylase (total and/or pancreatic) and/or lipase  $\geq 3X$  ULN
- characteristic findings of acute pancreatitis on computed tomography (CT) scan or magnetic resonance imaging (MRI).

If acute pancreatitis is suspected, appropriate laboratory tests (including levels of pancreatic amylase and lipase) should be obtained via the local laboratory. Imaging studies, such as abdominal CT scan with or without contrast, MRI, or gallbladder ultrasound, should be performed. If laboratory values and/or abdominal imaging support the diagnosis of acute pancreatitis, the subject must discontinue IP, and will be discontinued from the study after completing all ET and follow-up procedures. A review of the subject's medical data, including concomitant medications, should be conducted to assess potential causes of pancreatitis.

Each case of AE of pancreatitis must be reported. If typical signs and/or symptoms of pancreatitis are present and confirmed by laboratory values (lipase or amylase [total and/or pancreatic]) and imaging studies, the event must be reported as an SAE. For a potential case that does not meet all of these criteria, it is up to the investigator to determine the seriousness of the case (AE or SAE) and the relatedness of the event to IP.

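### Protocol Section 9.2.2.6 tells the investigator to replace stopped IP with another glucose-lowering drug, which does not fit a placebo-controlled trial in nondiabetic subjects

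*Protocol*

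**What the plan says.** Section 9.2.2.6 first allows IP to be interrupted when a severe or serious allergic reaction is suspected, and restarted if that is safe. Its last sentence covers permanent stopping: "If IP is permanently discontinued, the subject will receive another glucose-lowering treatment, judged by the investigator to be appropriate". It goes on to base that judgment on the individual's clinical status, and ends by discontinuing the subject from the study with a reference to Section 8.1.1.

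Section 8.1.1 lists a significant IP-related hypersensitivity reaction among the reasons for permanent discontinuation and states what follows: "Subjects who discontinue IP early will be also discontinued from the study after performing the ET visit and safety follow-up visit procedures". It mentions no substitute drug.

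Section 9.2.2.2 deals with another event that ends treatment for good. When laboratory values or imaging support acute pancreatitis, "the subject must discontinue IP, and will be discontinued from the study after completing all ET and follow-up procedures". No replacement drug is named there either.

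**The concern.** The sentence treats IP as glucose-lowering therapy whose loss has to be made good. That would make sense where subjects take the drug to control diabetes. Here nobody does.

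What is at stake is the care of an individual. Read literally, the sentence gives a person without diabetes, who has just had an allergic reaction and may have been on placebo, a drug for which the protocol states no indication. The protocol's view that hypoglycaemia is unlikely (Sections 3.3 and 7.4.1.1) rests on how incretins act. The sentence names no drug class, so that reasoning need not carry over to the replacement, and Section 3.3 plans no glucose self-monitoring. An investigator who sensibly gives nothing is left departing from the protocol's wording.

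**Working it through.** There is no figure in the plan to reproduce. The check is to set the sentence beside the rest of the protocol.

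1. **Who is enrolled.** Section 5.4 limits the trial to nondiabetic obese subjects. Exclusion [13] removes anyone with a diagnosis of any form of diabetes, or with screening glucose or HbA1c in the diabetic range.

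2. **What they take at entry.** Exclusion [30] removes anyone treated with a glucose-lowering agent in the 3 months before screening or between screening and randomization. No eligible subject therefore has a recent glucose-lowering regimen to which a new drug would be a successor.

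3. **What IP is for here.** The aim is mechanistic: energy expenditure and food intake. Section 3.3 expects no direct health benefit to subjects. Stopping IP does not leave a treated hyperglycaemia untreated.

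4. **What a placebo subject loses.** Section 7.2 randomizes 1:1. With up to 56 subjects, 56/2 = 28 would be on placebo. For them there is no active drug for another one to replace.

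5. **Whether the sentence makes treatment optional.** The verb is an unconditional future. The appropriateness phrase is attached to the treatment, so its natural reading is that the investigator chooses which drug suits the subject's status. A reading under which none is suitable is possible, but the sentence does not say so.

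6. **Whether another section requires or corrects it.** Section 8.1.1 requires only the early termination and safety follow-up procedures. Section 9.2.2.2, also a permanent stop, matches Section 8.1.1 and adds no drug. No other section modifies or withdraws the instruction.

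7. **How often it could apply.** The documents give no rate of permanent discontinuation for hypersensitivity, so none is calculated. Two exclusions make it uncommon: [27], "Have a history of atopy or clinically significant multiple or severe drug allergies", and [34], "Have previous exposure to tirzepatide or known allergies to tirzepatide or GLP-1 receptor agonists".

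**The case against.** The best defence is the clinical-status qualifier. An investigator facing a normoglycaemic subject could reasonably conclude that no glucose-lowering drug is appropriate and give none. Some subjects might also warrant one: inclusion [1] admits people with impaired glucose tolerance. Several safeguards limit harm: hypoglycaemia training (Section 3.3), discretionary glucose monitoring (Section 7.4.1.1) and recording of all medication (Section 7.7). This lowers the practical risk. It does not make the sentence right, because the qualifier does not clearly permit giving nothing.

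Several stronger readings are tempting, and the documents do not support them.

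- *That the sentence contradicts Section 7.7.* The ban on glucose-lowering agents there covers the treatment period, which is over for the subject once IP is permanently stopped. The general rule is "Additional drugs are to be avoided during the study unless required to treat an AE or for the treatment of an ongoing medical problem", and a subject with impaired glucose tolerance might meet its last condition. Section 8.2 also places study discontinuation before any new agent effective for the study indication; that would cover some replacement drugs, though not all. At most there is a tension.
- *That it contradicts Section 8.1.1.* That section is silent on replacement drugs; it does not forbid them.
- *That the calcitonin rule in Section 9.2.2.3 is a second comparator.* IP stopped under that rule may be restarted if calcitonin falls, so its silence on a replacement shows little. Pancreatitis is the like-for-like case.
- *That blinding is the core problem.* Section 7.3 says "all study site personnel, except site staff who dispense and administer study medication, will be blinded to treatment allocation", but whether a subject needs a glucose-lowering drug depends on glycaemia, and emergency unblinding is available if medical management requires it.

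**Conclusion.** The instruction is wrong as written for this population and should be corrected. It directs a replacement for a therapy that IP does not provide in this trial and that placebo subjects never had. The conclusion rests on reading the qualifier as governing the choice of drug more naturally than the decision to treat; the opposite reading is possible, which is a further reason to make the text plain.

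The size is small. It concerns subject management and safety in few or no subjects; a single case would be 1/56 = 1.8% of those randomized. A reader might infer that results could be biased. They could not be by this route: the subject leaves the study under Section 8.1.1 in any event, and neither the Week 18 comparison of sleep metabolic rate nor the sample size depends on the sentence. Nor do the documents show that any subject would in fact be given an unneeded drug, since that requires both a permanent stop for hypersensitivity and an investigator who follows the literal wording. Severity: minor.

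**What to change.** Replace the last sentence of Section 9.2.2.6 with:

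*If IP is permanently discontinued, the subject will be treated as clinically indicated and will be discontinued from the study after the ET and safety follow-up visits (Section 8.1.1).*

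This leaves the investigator free to treat the reaction, and to give a glucose-lowering drug to an individual who needs one, without directing it for everyone. It also brings the section into line with Sections 8.1.1 and 9.2.2.2. No other section needs to change. The cost is one sentence in a non-substantial amendment, the category the sponsor used for amendment (f), with no effect on data collection, sample size or any analysis.

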#### **9.2.2.7. Injection-Site Reactions**

Injection-site assessments for local tolerability will be conducted, when reported as:

- an AE from a subject, or
- a clinical observation from an investigator.

Reported injection-site reactions will be characterized within the following categories:

- edema
- erythema
- induration
- itching
- pain

Injection-site reactions will be collected on the eCRF created for these events. At the time of AE occurrence, unscheduled samples may be collected for measurement of tirzepatide ADA and tirzepatide concentration if the event is suspected to be immune related by the investigator.

All injection-site reactions reported as AEs will be closely monitored until resolution. The report of a clinically significant AE of injection-site reaction may prompt notification of the sponsor, clinical photography, and referral for dermatologic evaluation and consideration of a skin biopsy and laboratory evaluations (ALT, AST, complete blood count with percent eosinophils, and additional immunogenicity testing).

Site staff will be provided with separate instructions/training on how to evaluate injection-site reactions and their severity in a consistent manner. Photographs of injection-site reactions may be taken in a standardized manner for record-keeping purposes; however, the photographs will not be used to evaluate the severity of injection-site reaction.

#### **9.2.2.8. Hepatobiliary Disorders**

All events of treatment-emergent biliary colic, cholecystitis, or other suspected events related to gallbladder disease should be evaluated and additional diagnostic tests performed, as needed. In cases of elevated liver markers, hepatic monitoring should be initiated as outlined in Section 9.4.5.1 (Hepatic Safety) and [Appendix 4](#).

#### **9.2.2.9. Severe Gastrointestinal Adverse Events**

Tirzepatide may cause severe GI AEs, such as nausea, vomiting, and diarrhea. Information about severe GI AEs as well as antiemetic/antidiarrheal use will be collected in the AE form of the eCRF. For detailed information concerning the management of GI AEs, refer to Section 7.7.1 (Management of Subjects with Gastrointestinal Symptoms).

#### **9.2.2.10. Acute Renal Events**

Renal safety will be assessed based on laboratory renal functional assessment as well as assessment of AEs suggestive of acute renal failure or worsening of chronic renal failure. Subjects with GI AEs, including nausea, diarrhea, and vomiting are at increased risk of developing dehydration. Dehydration may cause a deterioration in renal function, including acute renal failure. Subjects should be advised to notify investigators in case of severe nausea, frequent vomiting, or symptoms of dehydration.

#### **9.2.2.11. Major Depressive Disorder/Suicidal Ideation Monitoring Using the C-SSRS and PHQ-9 Questionnaires**

Overweight and obese patients are at an increased risk of depression (Luppino et al. 2010). Depression can increase the risk of suicidal ideation and behavior. Therefore, study subjects will be screened at trial entry and monitored during the study for depression, and suicidal ideation and behavior.

Baseline and treatment-emergent assessment of depression, suicidal ideation, and behavior will be monitored during the study using the C-SSRS and PHQ-9 as specified in the Schedule of Activities (Section 2). Before administering the C-SSRS or the PHQ-9, study site personnel will question the participant about any change in the preexisting condition(s) and the occurrence and nature of any AEs. These questionnaires should be administered after assessment of AEs. For this study, the C-SSRS is adapted for the assessment of the ideation and behavior categories only. The Intensity of Ideation and Lethality of Behavior sections are removed.

Nonserious AEs obtained through the questionnaire are recorded and analyzed separately. Only *serious* AEs elicited through the C-SSRS or PHQ-9 are to be recorded as AEs via the eCRF and reported to Lilly or its designee within 24 hours as SAEs.

The C-SSRS (Columbia Lighthouse Project [WWW]) is a scale that captures the occurrence, severity, and frequency of suicidal ideation and/or behavior during the assessment period. The scale includes suggested questions to solicit the type of information needed to determine if suicidal ideation and/or behavior occurred. The tool was developed by the National Institute of Mental Health trial group for the purpose of being a counterpart to the Columbia Classification Algorithm of Suicide Assessment categorization of suicidal events.

The PHQ-9 is a validated self-report screening tool that assesses the presence and intensity of depressive symptoms. The PHQ-9, which incorporates the 9 Diagnostic and Statistical Manual-IV depression criteria as “0” (not at all) to “3” (nearly every day), was developed for use in primary care settings (Kroenke et al. 2001).

